8.8 Flow chart of trial procedures

Figure 5 Flow chart ARON project

Figure 6 flow chart trial procedures

8.9 Qualitative assessments – Nested studies

A process evaluation will be nested within the pragmatic clustered randomized trial. The process evaluation will capture data to understand how the intervention is used and viewed by physicians and patients. This is important for informing implementation in practice. It will explain how physicians and patients experience the intervention. We aim to identify factors within each arm which influence the behaviour to prescribe antibiotic treatment whilst taking part in the intervention arm or whilst receiving usual care in order to build a framework describing the mechanisms required for successful implementation.

Individual telephone interviews will be conducted with physicians and parents taking part in the trial. Interviews will be carried out to capture perceived barriers and facilitators to using the diagnostic algorithm including POC CRP testing approach or with the usual care approach. Physicians (approximately 16, minimum 8 French-speaking and 8 Flemish-speaking) will be purposively sampled to obtain variation in gender, practice setting and experience. Parents (approximately 14-18) will be purposively sampled to obtain variation in age, age and the number of children, socio-demographic background, gender and whether they received antibiotics. Interviews will follow semi-structured topic guides exploring physicians' and parents' views and experiences of taking part in the trial. These individual telephone interviews will be performed with a selection of parents to address whether their concerns were discussed appropriately and whether their expectations were met and how they experienced the consultation and/or POC CRP testing.

Topic guides will be informed by existing literature and theory of health behaviour to ensure that questions elicit likely key determinants of behaviour. Topic guides will be piloted with patient representatives and clinicians. Interviews will be carried out by telephone and analysed using thematic and Framework analysis. These telephone interviews will indeed be performed by someone with the required skills and expertise in qualitative methods. This nested study will also be submitted for ethical review as an amendment to the main trial protocol.

8.10 Withdrawal criteria

Withdrawal from the study can be initiated either by the child, their parents or by the physician.

As stated in the Informed Consent, children and their parents have the right to end her/his participation in the trial at any point in time and for any reason. In case a child or parent wishes to end her/his participation, she/he can do so either by notifying her/his physician.

The treating physician can also consider a child for withdrawal from the study. However, the physician will have to discuss this option with the study coordinator and to receive the consent of the latter before the final decision of withdrawal can be made.

In all instances, the reason for withdrawal will be asked for and notified.

Withdrawn children will not be replaced.

8.10.1 Discontinuation of trial follow-up

If the follow-up is stopped early, the reason should be recorded in the patient's health records and be reported on the appropriate CRF whether it is due to either the patient's, parent/legal guardian's or clinician's decision. Reasons for stopping protocol treatment may include, but are not limited to:

• The patient and/or patient's parent/guardian does not wish to continue with further trial follow-up.

The trial will be analysed on an intention-to-treat (ITT) basis and all patients who stop follow-up will remain in the trial unless the patient and/or parent/legal guardian explicitly withdraws consent for data collection.

8.10.2 Discontinuation of trial procedures (if applicable)

Patients who discontinue trials procedures will be included in the final analyses of the primary outcome as these are registered at the baseline consultation, given informed consent was obtained.

8.10.3 Withdrawal of consent (discontinuation of trial participation)

The patient and/or parent/legal guardian may withdraw consent at any time during the study. For the purposes of this trial, withdrawal is defined as:

 The patient and/or parent/legal guardian would like to withdraw consent from study and is not willing to be followed up for the purposes of the trial at any further visits (i.e. only data collected prior to the withdrawal of consent can be used in the trial analysis).

The details of withdrawal should be clearly documented in the patient's health records and in the eCRF.

8.10.4 Loss to follow-up

If a patient is lost to follow-up, every effort should be made to contact the patient's physician to obtain information on the patient's status. Similarly, if a patient's care is transferred to another clinician, every effort should be made so that follow-up information will be obtained.

8.11 End of trial

End of a trial means the last visit of the last child, including collection of the follow-up data up to 30 days after the index consultation.

Where necessary, end of trial documents and notifications will be drafted and presented.

9 TRIAL INTERVENTION

Care as usual

In the control arm, patients will receive 'usual care' left at the discretion of the treating physician.

Apart from the general training session for all participating physicians they have attended prior to recruitment and randomization, physicians in the control arm will not receive additional tools.

They are expected (but not forced) to follow the Belgian guidelines (as described in "BAPCOC National guidelines and the RIZIV consensus meeting "Rational use of antibiotics in children"). (Figure 2)

9.1 Name and description of intervention(s)

Intervention: diagnostic algorithm

Guidance will be part of a **diagnostic algorithm** which includes **clinically guided POC CRP** testing and **safety netting advice** to inform parents on what to expect and what to look out for.

The safety-netting advice will be supported by a parent information booklet, based on previous research (the "When should I worry"-interactive booklet (a guide to Coughs, Colds, Earache & Sore Throats), the "Mijn kind heeft koorts" booklet (Eefje de Bont, www.thuisarts.nl), and the "Caring for children with coughs"-leaflet (information about how to look after a child who has a cough and when to see the doctor)).

They are expected (but not forced) to follow the Belgian guidelines (as described in "BAPCOC National guidelines and the RIZIV consensus meeting "Rational use of antibiotics in children"). (Figure 2)

9.2 Legal status of the intervention

The trial is being carried out under a Clinical Trial Authorisation (CTA). The POC CRP device is therefore only to be used by the named investigators, for the patients specified in this protocol, and within the trial.

9.3 Assessment of compliance

The follow-up will not contain any patient identifiable information (of the child or parent). A built-in system will be developed for the follow-up app allowing to track users as they register daily follow-up. Furthermore, each time the user performs specific actions (such as filling in the diary, answering questions etc.) this will be recorded.

10 SAFETY RECORDING AND REPORTING

The risk of adverse events occurring as a consequence of the intervention in this trial is unlikely therefore safety reporting will be limited to the safety reporting that is necessary in routine care (https://www.fagg-afmps.be/nl/notification_effets/humane_geneesmiddelenbewaking/melding_gezondheidszorgbeoefenaars).

Any safety events related to the device, which is CE marked and used within the intended use, will follow the usual reporting/materiovigilance requirements.

All safety parameters (e.g. mortality, admission to hospital) are collected in the eCRF and are prioritized over other follow-up data and monitored by the academic research team (monthly remote follow-up contact) and data managers. Any potential safety events detected by means of the follow-up data as part of the eCRF will be assessed during the regular trial steering committee meetings after the first winter season and then annually.

11 STATISTICS AND DATA ANALYSIS

11.1 Sample size calculation

11.1.1 Initial sample size calculation before the start of the trial

Primary outcome

The main aim of our study is to establish the assumed superiority of a **diagnostic algorithm** including a standardized clinical assessment, a POC CRP test, and safety netting advice over usual care to reduce **antibiotic prescribing rates**.

Previous research in a similar population has shown approximately **17%** of children testing positive if yes to any of three features: clinician gut feeling, dyspnea and body temperature ≥40°C. (12) In all children, **30.43%** will be prescribed antibiotics.(22)

The outcome(s) on which the sample size calculation is based is the antibiotic prescribing rate at the first contact baseline consultation.

In children testing positive on the clinical decision tree, we found in the ERNIE2 trial (22), that:

- CRP was <5 mg/L in 28% of children testing positive on the clinical decision tree
- CRP was ≥5mg/L in 72% of children testing positive on the clinical decision tree
- of children testing positive on the clinical decision tree with CRP <5 mg/L: 29% received antibiotics, in 24% evidence-based guidelines advised to prescribe antibiotics and in 67% evidence-based guidelines advised to withhold antibiotics
- of children testing positive on the clinical decision tree with CRP ≥5 mg/L: 62% received antibiotics, in 47% evidence-based guidelines advised to prescribe antibiotics and in 53% evidence-based guidelines advised to withhold antibiotics

- of children testing negative on the clinical decision tree with CRP <5 mg/L: 11% received antibiotics, in 10% evidence-based guidelines advised to prescribe antibiotics and in 90% evidence-based guidelines advised to withhold antibiotics
- of children testing negative on the clinical decision tree with CRP ≥5 mg/L: 38% received antibiotics, in 23% evidence-based guidelines advised to prescribe antibiotics and in 74% evidence-based guidelines advised to withhold antibiotics

If a diagnostic algorithm including the clinical decision tree, POC CRP test and safety netting advice is provided, we can prudently assume to expect antibiotic prescribing rate in all children to be reduced to 22.65% in the intervention arm, based on our systematic review ([name] et al., BMJ Open 2019), the previous trials in acutely ill children and a previous systematic review in adults.

For each of the outcomes stated above the following target difference is important for the key stakeholder groups consulted (e.g. patients, clinician, and healthcare funder): from 30.43% to 22.65%.

Using a 5% significance level (alpha 0.05), an intracluster correlation coefficient (ICC) of 0.063 (based on data from the ERNIE2 study in the exact same population), and power of 90% (beta 0.1), this would require **55 clusters of 50 patients** in both arms, resulting in **5500 children**. Drop-outs are unlikely to be a large problem since there will be only 1 study visit complemented by the collection of follow-up information. Imputation of missing values for patient-and/or parent/legal guardian-reported outcomes (if there are any) will be considered. Other outcomes will be collected in the patient health record of the physician.

R code:

We used the n4props-function in the R package CRTSize, using the following command:

n4props(0.3043,0.2265,50,0.063, alpha = 0.05, power=0.9, AR=1, two.tailed=TRUE, digits=3)

Considering the pragmatic nature of this trial and in correspondence with the 10% of practices performing nonconsecutive inclusion of patients (high risk of selection bias) during the ERNIE2 trial, we will perform sensitivity analyses only considering physicians who have recruited a minimum of 10 patients per year. Taking into account the required sample size for this analysis of the primary study outcome as part of the sensitivity analysis, these assumptions result in a total sample size of 6111 patients for the primary study outcome.

Secondary outcomes

To demonstrate non-inferiority in the effect of the diagnostic algorithm including the **clinical decision tree**, **POC CRP test and safety netting advice** on the **secondary outcomes**, we use the following assumptions (based on observed proportions in previous trials in children) (11,27):

Secondary outcome		Proportion in intervention group	Proportion in usual care group	Means + pooled standard deviation (SD)	Clinically significant change*
1.	Time to clinical recovery (days)	NA	NA	Mean intervention group: 4.06 Mean usual care group: 4.15 Pooled SD: 3.89	1
2.	Additional investigations at index and/or during follow-up (%)	9.0%	9.8%	NA	3%
3.	Re-consultations during follow-up (%)	33%	34%	NA	4%
4.	Antibiotic prescribing rate during follow up (%)	7%	8%	NA	2%

* based on consensus from a group of clinical researchers with experience in diagnostic and clinical research

NA: not applicable

The non-inferiority limit for the above 4 secondary outcomes is 1 day, 3%, 4%, and 2%, respectively, i.e. the intervention will be deemed non-inferior if the difference between the allocated groups (intervention – control) is less

than 1 day, 3%, 4%, and 2%, respectively. Therefore, the intervention will be deemed non-inferior if the upper limit of the 95% confidence interval lies below 1 day, 3%, 4%, and 2%, respectively.

Sample size for comparison of 2 means (for the first secondary outcome: time to full clinical recovery) and 2 proportions (for the other three secondary outcomes) for a non-inferiority trial was calculated with the following assumptions:

- 1-β = 0.80
- Allocation ratio (intervention/usual care) = 1
- Design effect (DE) = 1 + ρ(n-1)
- n = number individuals per cluster
- ρ = intracluster correlation coefficient
- · We account for the clustering at the level of the individual physician
- n = 50 patients per cluster
- ρ = 0.025 (Previous studies have illustrated that in primary care ICCs for clinical outcomes are lower than those for process outcomes and the ICC for adverse effects to be around 0.025)(28)
- Resulting DE = 2.225
- to account for multiple testing (n=4), we have applied the Bonferroni-Holm correction, generally considered to be a rather conservative approach to control the family-wise error rate.(29) Therefore, our significance levels for the 4 secondary outcomes were 0.0125 (α /4), 0.167 (α /3), 0.025 (α /2), and 0.05 (α /4), respectively.

Secondary outcome		Preliminary sample size	Significance level (α)	Design effect (DE)	Total sample size (preliminary sample size * DE) for this outcome
1.	Time to clinical recovery (days)	575	0.0125	2.225	1280
2.	Additional investigations at index and/or during follow-up (%)	2079	0.0167	2.225	4626
3.	Re-consultations during follow-up (%)	2312	0.025	2.225	5144
4.	Antibiotic prescribing rate during follow up (%)	1906	0.05	2.225	4240

Taking into account the required sample size for these analyses of the primary study outcome and the secondary outcomes, aiming to recruit a **total sample size of 6111 patients** will be sufficient. Considering we previously recruited 8962 and 3981 acutely ill children in Belgium, this seems feasible.

11.1.2 impact of Covid on the primary outcome and revised sample size calculation during the trial

The S62005 ARON trial was planned before the COVID-19 pandemic. Though, the trial actually started in the initial part of the pandemic, just as the Delta variant (second wave) was first emerging: early 2021. The ARON trial kept going through all subsequent COVID-19 waves and is currently still ongoing.

The COVID-19 pandemic has shown that antibiotic prescribing has (for the better) declined during the pandemic, as shown by several studies and reports:

- https://www.ecdc.europa.eu/en/news-events/reported-decrease-antibiotic-consumption-across-eueea- during-covid-19-pandemic

KCE Trials programme

This has urged us to revise our sample size calculation, based on the overall prevalence found in the first patients recruited, given the start of our trial during the pandemic.

This amendement concerns a clarification of the impact the COVID-19 pandemic has had on recruitment as well as the overall prevalence of our primary outcome, the antibiotic prescribing rate in children.

AIMS

With this amendment, we aim to:

- (1) investigate the influence of the COVID-19 pandemic on antibiotic prescribing rates in practices included in the ARON trial and (2) redetermine the required sample size for the ARON trial.
- (3) monitor whether inclusions were done consecutively, as per the study protocol, in order to minimize selection bias.

METHODS

1. Audit of antibiotic prescribing rate before and during the COVID-19 pandemic

An audit is an official methodical examination and review, typically of an organisation's or individual's accounts or financial situation¹. In the context of this appendix, we aim to audit practices' antibiotic prescribing rates in a timematched before-after manner. We will compare the rate before the COVID-19 pandemic (before, Figure 1) and during the COVID-19 pandemic (after, Figure 2), in an identical period during the year (Figure 1). A statistically significant change from baseline quantified by odds ratios will indicate a change in antibiotic prescribing behaviour due to COVID-19. This audit will be executed by the study coordinator (SC) that manages the practice.

The audit questions are presented in Figure 7 and Figure 8.

ARON 1.Jaar 2018: alle kinderen 6maanden – 12 jaar die een contact hebben gehad bij de huisarts. a.Over hoeveel kinderen ging het

Is gelijk aan Consultatie
ls gelijk aan
um Is kleiner dan of gelijk aan 30/06/2017
ls groter dan of gelijk aan 01/01/2018
Is kleiner dan of gelijk aan 31/12/2018
um is groter dan of gelijk aan 01/01/2006

ARON 1.Jaar 2018: alle kinderen 6maanden – 12 jaar die een contact hebben gehad bij de huisarts b.Hoeveel kinderen hebben minstens 1 AB voorschrift gekregen (matched 1 mei 2017 t/m 30 nov 2018)

Patiëntenadministratie	Geboortedatum	ls groter dan of gelijk aan	01/05/2005
Contact	Туре	ls gelijk aan	Consultatie
Patiëntenadministratie	Geboortedatum	Is kleiner dan of gelijk aan	31/12/2016
Contact	Datum	Is kleiner dan of gelijk aan	30/11/2018
Contact	Datum	ls groter dan of gelijk aan	01/05/2017
Contact	Auteur	ls gelijk aan	
Medicatie	Datum	Is kleiner dan of gelijk aan	30/11/2018
Medicatie	BCFI boom	ls gelijk aan	Antibacteriële middelen
Medicatie	Datum	ls groter dan of gelijk aan	01/05/2017

¹ Merriam-Webster dictionary. https://www.merriam-webster.com/dictionary/audit. Accessed 9 January 2023.

ARON 2.En de periode dat ze gerekruteerd hebben tijdens de trial (gemakkelijk te vinden in Redcap fictief voorbeeld 1 mei 2021 t/m 30 november 2022). a.Over hoeveel kinderen ging het

Patientenadministratie	Geboortedatum	Is kleiner dan of gelijk aan	30/11/2020			
Patiëntenadministratie	Geboortedatum	ls groter dan of gelijk aan	01/05/2009			
Contact	Auteur	ls gelijk aan				
Contact	Туре	Is gelijk aan	Consultatie			
Contact	Datum	Is groter dan of gelijk aan	01/05/2021			
Contact Datum Is kleiner dan of gelijk aan 31/10/2022 ARON 2.En de periode dat ze gerekruteerd hebben tijdens de trial (gemakkelijk te vinden in Redcap - bv 1 mei 2021 t/m 30 november 2022). b.Hoeveel kinderen hebben minstens 1 AB voorschrift gekregen						
Medicatie	BCFI boom	ls gelijk aan	Antibacteriële middelen			
Contact	Datum	ls kleiner dan of gelijk aan	31/10/2022			
Patiëntenadministratie	Geboortedatum	ls kleiner dan of gelijk aan	30/11/2020			
Contact	Datum	ls groter dan of gelijk aan	01/05/2021			
Medicatie	Datum	ls groter dan of gelijk aan	01/05/2021			
Patiëntenadministratie	Geboortedatum	ls groter dan of gelijk aan	01/05/2009			
Contact	Auteur	ls gelijk aan				
Contact	Туре	ls gelijk aan	Consultatie			
Medicatie	Datum	ls kleiner dan of gelijk aan	31/10/2022			

Figure 8. Audit questions (after start of the trial) in CareConnect software (Corilus).

Most software packages, e.g., CareConnect², Daktari³, HealthOne⁴, of which the former dominate the market, have a statistics/search module. This allows for easy and uniform access to the required data.

2. Sample size calculation

The original sample size calculation was based on previous data, assuming an overall prescribing rate of 26.5% in those children recruited for our trial.

The overall prevalence was found to be 18% overall in children recruited in the first 4938 patients recruited in the ARON trial.

If we were to assume a reduction of 5.3% (proportionate to our original reduction) between the usual care group and the intervention group, using a 5% significance level (alpha 0.05), an intracluster correlation coefficient (ICC) of 0.063 (based on data from the ERNIE2 study in the exact same population), and power of 90% (beta 0.1), this would require **63 clusters of 50 patients** in both arms, resulting in **6300 children**.

R code:

We used the n4props-function in the R package CRTSize, using the following command:

n4props(0.2065,0.1435,50,0.063, alpha = 0.05, power=0.9, AR=1, two.tailed=TRUE, digits=3)

Considering the pragmatic nature of this trial and in correspondence with the 10% of practices performing nonconsecutive inclusion of patients (high risk of selection bias) during the ERNIE2 trial, we will perform sensitivity analyses only considering physicians who have recruited in a consecutive way. Taking into account the required sample size for this analysis of the primary study outcome, these assumptions result in a total sample size of 7000 patients for the primary study outcome.

3. Non-consecutive recruitment

In the protocol, we have specified: "The participating physicians will be asked to consecutively recruit children with an acute illness over the recruitment period covering two winter seasons."

We wanted to further clarify what is meant by non-consecutive recruitment, by stating that GPs are likely to breach this assumption if:

- They recruit less than 10 patients per year
- ² CareConnect General Practitioner, Handleiding, Extra/tandwiel, Statistiek. https://careconnectmanual.corilus.be/nl/node/98. Accessed 10 January 2023.

³ Daktari gebruikersandleiding, "5.4 Geavanceerd zoeken". https://www.daktari.be/files/Daktari-handleiding.pdf. Accessed 10 January 2023.

⁴ HealthOne, Basis Handleiding. https://www.dropbox.com/s/4fwlwvr56z0wlw8/Basis%20handleiding.pdf?dl=0. Accessed 10 January 2023.

- They perform a point-of-care CRP test on nearly all (>90%) of the included children
- They deliberately only include children (>90%) that do not need antibiotics and exclude those that might need antibiotic treatment.

All of the above circumstances introduce significant selection bias and reduce the generalisability of our findings. Although we plan to perform an intention-to-treat analysis given the pragmatic nature of our trial, protocol violations caused by the inappropriate inclusion/exclusion of patients will be far more detrimental for the validity of our trial. Apart from the intention-to-treat analysis a per protocol sensitivity analysis will be performed.

The abovementioned assumptions can be tested, based on:

- the qualitative sub-study (semi-structured interviews with parents and physicians) in a selection of the recruiting practices
- the audit as described above
- monitoring visits by the clinical trial centre supporting data monitoring of the ARON trial

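### The re-consultation sample size does not follow from its printed inputs, and 80% non-inferiority power is not assured for three secondary outcomes sized with an adverse-effect ICC

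*Protocol*

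**What the plan says.** Protocol 11.1.1, under secondary outcomes, sets 80% power, 1:1 allocation and a single ICC of 0.025 for all four outcomes. The support offered is that "Previous studies have illustrated that in primary care ICCs for clinical outcomes are lower than those for process outcomes"; the number itself is the one the protocol attributes to adverse effects. With "n = 50 patients per cluster" the design effect is 2.225. The table then gives these preliminary and total sizes:

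- additional investigations: 2079, total 4626
- re-consultation: 2312, total 5144
- follow-up antibiotic prescribing: 1906, total 4240

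The section concludes, "Taking into account the required sample size for these analyses of the primary study outcome and the secondary outcomes", that 6111 children are enough.

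For the primary outcome, antibiotic prescribing at the index consultation, the same section uses "an intracluster correlation coefficient (ICC) of 0.063 (based on data from the ERNIE2 study in the exact same population").

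Protocol 11.1.2 and the SAP's sample size section raise the target to 7000 on the primary outcome alone. Neither returns to the secondary sizes or their ICC.

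**The concern.** There are two separate problems.

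**ICC.** The value comes from adverse effects, and the sentence that supports it says process outcomes cluster more strongly. Ordering tests and prescribing are clinician decisions, and re-consultation is use of care. Follow-up prescribing is defined in Protocol 4.2.4 in the same terms as the primary outcome (an immediate or delayed prescription), yet it gets 0.025 where the primary gets 0.063. No reason is given for the difference.

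**Arithmetic.** One of the three proportion rows does not come out of its own inputs, whatever ICC is used.

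The research question is whether prescribing can be reduced safely. Protocol 4.1 says any reduction must be read alongside these secondary outcomes, so they are the formal tests behind the word safely. If power is lower than stated, a failure to show non-inferiority may reflect sample size, and a reader relying on the protocol's sufficiency statement would not know it.

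**Working it through.** **Inputs (Protocol 11.1.1).** Rates are intervention vs control: investigations 9.0% vs 9.8%, margin 3%, alpha 0.0167 (the table's value; the text prints 0.167); re-consultation 33% vs 34%, margin 4%, alpha 0.025; follow-up antibiotics 7% vs 8%, margin 2%, alpha 0.05. Power is 0.80 and cluster size 50. The protocol does not say whether alpha is one- or two-sided; one-sided levels reproduce its figures.

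**Formulas.** Let v = p_I(1−p_I) + p_C(1−p_C) and d = margin + p_C − p_I.

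- Total before clustering: n = 2(z_{1−α} + z_{0.80})² v / d²
- DE = 1 + 49 × ICC, which is 2.225 at 0.025 and 4.087 at 0.063
- Power at N children: Φ( d / √(2v·DE/N) − z_{1−α} )

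**Step 1: the protocol's own figures.**

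- Investigations: 2 × (2.1272 + 0.8416)² × 0.170296 / 0.038² = 2079.0 (stated 2079)
- Follow-up antibiotics: 2 × (1.6449 + 0.8416)² × 0.1387 / 0.03² = 1905.6 (stated 1906)
- Re-consultation: 2 × (1.9600 + 0.8416)² × 0.4455 / 0.05² = 2797.3, so 2798 (stated 2312)

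Multiplying by 2.225 is done correctly in all three rows. For re-consultation, none of these variations gives 2312: one- or two-sided alpha, power 0.80 or 0.90, other variance forms, the assumed benefit credited, set to zero or reversed, per arm or total. The figure appears only if d is 5.5 points instead of 4 + 1 = 5.

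**Step 2: re-consultation at the protocol's ICC of 0.025.** 2798 × 2.225 is about 6,225, above 6111.

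- N = 6111: 6111/2.225 = 2746.5; standard error √(2 × 0.4455/2746.5) = 0.01801; 0.05/0.01801 − 1.960 = 0.816; power 79.3%
- N = 7000: 7000/2.225 = 3146.1; standard error 0.01683; 2.971 − 1.960 = 1.011; power 84.4%

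**Step 3: power at 7000 over an assumed ICC range** (cluster size 50, listed alphas).

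| ICC | Investigations | Re-consultation | Follow-up antibiotics |
|---|---|---|---|
| 0.025 | 93.6% | 84.4% | 93.9% |
| 0.03 | 91.0% | 80.5% | 91.7% |
| 0.04 | 85.1% | 73.1% | 87.0% |
| 0.05 | 79.0% | 66.5% | 82.1% |
| 0.063 | 71.5% | 59.2% | 76.2% |

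**Step 4: the largest ICC that keeps 80% at 7000,** (7000/n − 1)/49.

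- Investigations: (7000/2079 − 1)/49 = 0.048
- Re-consultation: (7000/2798 − 1)/49 = 0.031; if 2312 were right, 0.041
- Follow-up antibiotics: (7000/1906 − 1)/49 = 0.055

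At ICC 0.063 the totals needed are n × 4.087: 8,497, 11,435 and 7,790, all above 7000. Time to recovery is not affected: 575 × 4.087 = 2,350.

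**The case against.** **The value 0.063 is not an ICC for these outcomes.** It belongs to index prescribing. A reader might infer from the 0.063 row that the stated 80% power is missed for all three. The documents do not support that, because they give no ICC for any of the three, and 7000 exceeds each stated requirement with room to spare. This objection stands.

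**Binary ICCs depend on prevalence.** Assume practices vary as much on the logit scale for the rarer outcomes as for index prescribing. An ICC of 0.063 at the 26.5% prescribing rate then becomes about 0.032 at 9.4% (investigations) and 0.026 at 7.5% (follow-up antibiotics), with power at 7000 of 90% and 93%. Anchored at the 18% seen in the trial, it becomes 0.040 and 0.034, with power 85% and 90%. So treating follow-up prescribing as the same behaviour does not by itself contradict a value near 0.025. This also stands, as an assumption. It gives no comfort for re-consultation, whose rate of about 33.5% is above both anchors.

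**Classification.** The protocol does not label these outcomes as process or clinical. Section 4.1 presents them as checks for harm to the child, and re-consultation is largely started by parents. That makes 0.025 arguable, but the protocol does not make the argument.

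**Rounding.** Unrounded rates such as 32.8% and 34.3% would give about 2313. This is possible, but nothing in the documents supports it, and the other two rows reproduce from their printed rates. It is a reason to let the authors show their inputs.

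**6111 is superseded.** True. The shortfall there is under one percentage point of power, and at 7000 with ICC 0.025 re-consultation has 84.4%.

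**Conclusion.** The re-consultation row is wrong as printed: its inputs give 2798 (total about 6,225), not 2312 (total 5144). By the protocol's own ICC, the claim that 6111 suffices for this outcome narrowly fails, at 79.3% power. The current 7000 restores it to 84.4%.

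The ICC of 0.025 is poorly justified for outcomes 2 to 4, so their 80% power is not assured. It is not shown to be missed. Investigations and follow-up antibiotics tolerate roughly a doubling of the assumed ICC. Re-consultation does not: its power at 7000 drops below 80% once the ICC passes about 0.031, to 73.1% at 0.04 and 59.2% at 0.063.

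These figures assume 50 children per practice, the listed alphas as one-sided levels, the protocol's assumed small benefit, and no loss to follow-up. With 7000/122 = 57.4 children per practice, re-consultation power at ICC 0.025 is 81.5%. The 95% confidence interval rule in the same section corresponds to a one-sided 0.025. The re-consultation results are unchanged under it, but follow-up antibiotics would fall to 79.1% at ICC 0.04.

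**What to change.** 1. In Protocol 11.1.1, correct the re-consultation row to 2798 and a total of about 6,225, or state the unrounded inputs that give 2312.
2. Restate power for secondary outcomes 2 to 4 at the current 7000. Either show it over ICC 0.025 to 0.063, labelled as an assumed range with 0.025 as the favourable end, or use outcome-specific ICCs estimated blind to arm from children already recruited (4938 at the time of the revision).
3. Qualify the sufficiency statement accordingly, and carry the restated power into the SAP, whose sample size section covers only the primary outcome.

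This is a change to text and one table, plus a short blinded calculation if that route is taken. It needs no extra patients, visits or analyses, and leaves margins and error rates alone. The cost is a less favourable stated power, chiefly for re-consultation.
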